### 3. INVESTIGATIONAL PLAN

**Design.** This project is a feasibility pilot study to test the effects of vitamin C supplementation, and to obtain initial estimates of effect size to support a future RCT. The proposed vitamin C supplementation intervention study is a three-group, single blind, placebo controlled prospective design (control n=14, Vit C 500mg n=14, Vit C 1000mg n=14). The most commonly tested dose of vitamin C in current trials on vitamin C supplementation is 1 g/day. The primary endpoint to evaluate the effect of vitamin C supplementation is serum vitamin C level. The secondary outcomes include HF symptom burden, HRQOL, cardiac function, and oxidative stress. The variables would be measured in person at baseline and at 3 months include: HF symptom burden, HRQOL, PROMIS fatigue, depression and sleep disturbance, serum vitamin C level, biomarker of cardiac function (i.e., cardiac output using impedance cardiograph) and oxidative stress (8-iso-PGF2a isoprostane, see below in detail), as well as demographic, clinical, and other variables that can affect study outcomes (e.g., age, gender, race/ethnicity, body mass index, serum creatinine) and medications. HF symptom burden and HRQOL will also be measured at Month 1 and 2 by phone. We will also collect data to assess feasibility (recruitment, retention, attrition rates).

**Sample and Setting.** A total of 42 participants (14 per group) will be randomly assigned to either the control or the intervention group. Patients with HF will be recruited at the University of North Carolina Hospital internal medicine/cardiology outpatient clinics.

**Inclusion/Exclusion Criteria.** Inclusion criteria include patients (a) have a diagnosis of chronic HF. The diagnosis and etiology of chronic HF will be confirmed by a HF cardiologist using established criteria, (b) have undergone evaluation of HF and optimization of medical therapy, (c) are not taking any vitamin C supplementation at all or are willing to stop taking their current vitamin C supplementation, (d) able to read and speak English, (e) have >1 month from any inpatient hospitalization, (e) treating cardiology healthcare provider indicates the individual is a good candidate for this study that involves 3 months of vitamin C supplement of 500 mg/day, 1g/day, or placebo, (f) Per treating healthcare provider's assessment, patient's projected lifespan is greater than or equal to 6 months.

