### 4. INTERVENTION

The intervention is designed to complement medical management. Therefore, all patients will continue to be medically managed by their health care provider as usual.

Participants will have a visit at baseline and Month 3 (with some flexibility to do the final visit at 3 months +/- 1 month) coordinated with their regular clinic visits that are typically scheduled every 3 months.

**Vitamin C supplementation.** Throughout the study, patients will continue with their routine diets. Patients randomized to the intervention groups will be provided with 4-month supply of either Vitamin C 500mg or Vitamin C tablets (1000mg) in a bottle and the control group will be provided placebo tablets in a bottle. All participants in the intervention group will be instructed to take one vitamin C tablet (500mg/ day or 1000mg/day) with one meal daily from baseline for 3 months and all control group participants will be instructed to take one placebo tablet with one meal daily from baseline to 3 months. Participants will return their un-used investigational drugs on the day of their 3-month follow-up. We will count remaining pills to determine participant's treatment adherence with both the vitamin C supplementation (500mg or 1000mg) and control (placebo) groups. After counting the pills, the un-used pills will be delivered to the Investigational Drug Services (IDS) pharmacy to dispose. We will draw blood to measure serum vitamin C level to determine drug accountability.

**Role of the Investigational Drug Services (IDS).** The IDS will provide oversight for the storage, dispensing, labeling, distribution and disposal of all investigational medications (vitamin C tablets and placebo) for the study.

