## **5. PROCEDURES AND RECRUITMENT STRATEGY**

Permission for this study will be obtained from the University of North Carolina at Chapel Hill Institutional Review Board. A dedicated and trained research assistant will recruit HF patients from the UNCH clinics. A list of HF patients who will come to the UNCH clinics will be generated and obtained from the staff in charge for the scheduling information in the clinics one week before patients' visits. On the day that the potential participants come to the clinic, the research assistant will screen the potential participant's eligibility based on inclusion and exclusion criteria. The research assistant also will consult with the potential participant's treating healthcare provider to make sure the potential participant is appropriate for the study and patient's projected lifespan is greater than or equal to 6 months. Once the research assistant confirms the potential participants are eligible and gets approval from the provider, the research assistant will approach and briefly explain the study to recruit potential participants while they wait to see their physicians. If potential participants are interested in participation, the research assistant will then confirm eligibility. For eligible patients, study requirements will be explained in detail. If the patient agrees to participate, a signed informed consent will be obtained based on consent process (see below) and we will administer the survey, measure cardiac impedance and obtain the blood samples. All eligible patients will be randomized to either the control group or to the intervention group using the Medsharing application for clinical trials.

**Baseline visit.** Data on socio-demographics, clinical characteristics medications, symptom burden, PROMIS depression, fatigue, and sleep disturbance, HRQOL, will be collected at the beginning of the visit and blood will be drawn to measure serum vitamin C level and oxidative stress (8-iso-PGF2a isoprostane). All participants will be asked to return their respective supplementation bottles to the research assistant at Month 3. We will count pills to determine patient adherence to taking the placebo or vitamin C supplementation.

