**Follow up phone call (Month 1 and 2).** Follow up phone calls will occur within 1 week after enrollment to follow-up whether they are taking the investigational pills (vitamin C or placebo) daily and whether they have any adverse events from taking the investigational pills, as well as at Month 1 and 2. The research assistant will inquire about general welfare and collect data on HF symptom burden and HRQOL (for both groups).

***Month 3 visit.*** Data on socio-demographics, clinical characteristics medications, symptom burden, PROMIS depression, fatigue, and sleep disturbance, HRQOL, will be collected at the beginning of the visit and blood will be drawn to measure serum vitamin C level and oxidative stress (8-iso-PGF2a isoprostane). All participants will be asked to return their vitamin C (or placebo) bottle to the research assistant at Month 3. We will count pills to determine their adherence to taking the placebo or vitamin C supplementation.

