## 9. DATA MANAGEMENT AND STATISTICAL ANALYSIS

Each participant will be assigned an anonymous ID. Data will be collected using touchscreen laptop computer, and the REDCap (Research Electronic Data Capture) system, a secure web-based application that is designed to support data capture for research studies.

All data analyses will be performed using SPSS 24.0. All estimates will be obtained along with 95% confidence intervals.

Descriptive statistics: All data with approximately symmetric distributions will be described by their mean and standard deviation, as well as number/frequency and percentage (for Aim 3) and variables with skew will be described by the median and interquartile range. Categorical variables will be shown as total number and proportion and will include: race, sex, NYHA functional class, and comorbidity. Associations between categorical variables will be tested by the Chi Square test ( $X^2$ ) or McNemar's test. Continuous variables will include symptom burden, PROMIS depression, fatigue, and sleep disturbance, HRQOL, cardiac function, serum vitamin C levels and biomarker for oxidative stress. Associations between categorical and continuous variables will be tested by t-test and analysis of variance (ANOVA). Associations between continuous variables will be tested using Pearson's correlation coefficient ( $r$ ) will be used to establish if the correlation coefficient is statistically different.

Efficacy analysis for the specific aims is described below:

The primary endpoint is serum vitamin C level. For Aim 1 to test the effect of a vitamin C supplementation intervention on the primary outcome (serum vitamin C level) from baseline to 3-month follow-up among 3 groups, we will use repeated measure of ANOVA to detect differences in the serum vitamin C level from baseline to 3-month follow-up in the intervention group and compared to the control group from baseline to 3-month follow-up.

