The secondary endpoints are symptom burden, HRQOL, cardiac function, and oxidative stress. For Aim 2 to test the effect of a vitamin C supplementation intervention on the secondary endpoint of HF symptom burden from baseline to 3-month follow-up among 3 groups, we will use repeated measure of ANOVA to detect differences in symptom burden from baseline to 3-month follow-up in the intervention group and compared to the control group from baseline to 3-month follow-up. Similarly, to test the effect of a vitamin C supplementation intervention on the secondary endpoint of HRQOL (cardiac function, and oxidative stress) compared to the control group, we will use repeated measure of ANOVA to detect differences in HRQOL (cardiac function, and oxidative stress) from baseline to 3-month follow-up in the intervention group and compared to the control group from baseline to 3-month follow-up.

Similar analysis will be done for adverse events. to test the effect of a vitamin C supplementation intervention on the frequencies of adverse events compared to the control group, we will use ANOVA to compare frequencies of adverse events during the 3-month period among 3 groups.

Sample Size and Power: The total sample size of 42 participants will be selected as a pilot feasibility study. With 42 patients (14 in each group) and an alpha level of .05, the power of the ANOVA F test to detect a significant group difference will be 80% if the effect size is 0.5.

Interim/safety Analysis. We plan to conduct the interim/safety analysis when we have 50% of the intervention sample, and the findings (as well as adverse events) will be reported to the medical monitor. The medical monitor will make decisions about the safety of continuing (or stopping) the protocol, providing recommendations for recruitment, retention, safety, and other issues as appropriate.

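### Symptom burden and HRQOL: adjusting the Month 3 score for baseline would usually give a modestly tighter arm-versus-placebo estimate than the planned repeated-measures ANOVA, at no data cost

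*Combined protocol and SAP*

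**What the plan says.** Section 9 (Aim 2) states for symptom burden: "we will use repeated measure of ANOVA to detect differences in symptom burden from baseline to 3-month follow-up in the intervention group". For HRQOL, with cardiac function and oxidative stress in the same sentence, it states: "we will use repeated measure of ANOVA to detect differences in HRQOL (cardiac function, and oxidative stress) from baseline to 3-month follow-up". It names no covariate, no list of occasions, no model term and no contrast. Section 7 has covariates collected, but Section 9 gives them no role in a model.

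Section 3 adds two further occasions for the two questionnaires: "HF symptom burden and HRQOL will also be measured at Month 1 and 2 by phone". Sections 5 and 6 repeat this, so each scale is collected at baseline and at Months 1, 2 and 3.

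On purpose and reporting, Section 3 says the pilot is meant "to obtain initial estimates of effect size to support a future RCT", and Section 9 promises: "All estimates will be obtained along with 95% confidence intervals". Section 5 states that allocation is random: "All eligible patients will be randomized to either the control group or to the intervention group using the Medsharing application".

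**The concern.** A future trial needs an estimate of the difference between each vitamin C arm and placebo at Month 3, with its interval. Repeated-measures ANOVA treats the baseline score as another outcome. With two occasions it therefore compares change scores, which subtract the whole baseline difference whatever the strength of the link between baseline and Month 3. Regression adjustment subtracts only the share that the data support. With 14 patients per arm, any avoidable widening of the interval matters somewhat, and the baseline scores needed to avoid it are already collected.

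If all four occasions enter, baseline is still an outcome, and the test becomes a 6-df group-by-time interaction that does not target Month 3.

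**Working it through.** **The plan's own figure.** Section 9 gives 80% power for 42 patients, alpha .05 and effect size 0.5. Reading 0.5 as Cohen's f, a one-way ANOVA has noncentrality 0.5² × 42 = 10.5 on 2 and 39 df, and power 80.3%. The figure reproduces. It uses neither baseline nor repeated measures.

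**Inputs.** From the documents: 42 patients, 14 per arm, 3 arms. Assumed, because the documents do not give them: rho, and k = SD at Month 3 / SD at baseline. The reliability range in Section 7 (0.73-0.92) is not a three-month correlation.

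**Two-occasion reading.** Per-patient variances, in units of the baseline variance:

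- Change score: 1 + k² − 2k·rho.
- ANCOVA: k²(1 − rho²) × 38/37. The factor is 1 + 1/(42 − 3 − 2), the cost of estimating one slope.

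With slope b = k·rho, the change-score variance equals k²(1 − rho²) + (1 − b)². ANCOVA removes the second term and pays 1/37 for doing so. It therefore gains unless b is close to 1, and it can never lose more than 1/37 = 2.7% of variance (interval about 1% wider, since √1.027 = 1.013).

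**Equal SDs (k = 1).** The ratio ANCOVA/change is (1 + rho)/2 × 38/37. The 95% half-width for one arm against placebo is t × √(2/14 × variance), with 39 df for change and 38 for ANCOVA. At rho 0.5 this is 2.023 × √(2/14 × 1.00) = 0.765 against 2.024 × √(2/14 × 0.75 × 38/37) = 0.672.

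| rho | variance ratio | half-width, change / ANCOVA (SD units) | narrower by about |
|---|---|---|---|
| 0.5 | 0.770 | 0.765 / 0.672 | 12% |
| 0.6 | 0.822 | 0.684 / 0.620 | 9% |
| 0.7 | 0.873 | 0.592 / 0.554 | 6% |
| 0.8 | 0.924 | 0.484 / 0.465 | 4% |
| 0.9 | 0.976 | 0.342 / 0.338 | 1% |
| 0.95 | 1.001 | 0.242 / 0.242 | nil |

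Simulation (20,000 trials each) gave standard errors 12.5%, 9.7% and 6.8% smaller at rho 0.5, 0.6 and 0.7. In patients, 42/0.770 ≈ 55 and 42/0.873 ≈ 48 would be needed for change scores to match ANCOVA in 42. Those equivalents hold only for equal SDs.

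**Unequal SDs.** Variance ratio ANCOVA/change:

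| k | rho 0.5 | rho 0.6 | rho 0.7 | rho 0.8 |
|---|---|---|---|---|
| 0.8 | 0.587 | 0.619 | 0.645 | 0.657 |
| 1.2 | 0.895 | 0.947 | 0.992 | 1.024 |
| 1.25 | 0.917 | 0.967 | 1.007 | 1.027 |

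**Four-occasion reading.** Assume f = 0.5 in Month 3 SD units, equal SDs and correlations, and complete data. The interaction noncentrality is 10.5 × Σ(p − mean p)²/(1 − rho) on 6 and 117 df, where p is the share of the Month 3 effect present at each occasion. The sum is 0.75 if the effect is full from Month 1 and 0.556 if it grows linearly. For ANCOVA it is 10.5/[(1 − rho²) × 38/37] on 2 and 38 df.

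| rho | full from Month 1 | linear growth | Month 3 ANCOVA |
|---|---|---|---|
| 0.5 | 84.1% | 69.6% | 89.8% |
| 0.7 | 97.9% | 91.8% | 97.8% |
| 0.8 | 99.9% | 98.9% | 99.8% |

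Standard repeated-measures ANOVA also drops anyone who misses one contact. If each follow-up is missed independently with probability 8% (an assumption), 42 × 0.92³ ≈ 33 are complete, against 42 × 0.92 ≈ 39 with a Month 3 score. Under pure dropout the two counts are the same.

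**The case against.** The strongest reply is that nothing here is wrong. The endpoints are secondary, the study is a pilot, and the interval is wide under either method: at rho 0.7 the half-width moves from 0.592 to 0.554 SD. The size of the gain rests on a correlation and SDs that the documents do not give, and a somewhat larger Month 3 SD can erase it. All of this stands, and it sets the size of the point. It does not remove it, because the possible loss is capped at about 3% of variance while the gain is several times that over much of the plausible range.

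It is also fair to say that the Aim 2 wording most naturally means two occasions, in which case the four-occasion criticisms do not arise. That reading, however, leaves the Month 1 and 2 scores without a stated analysis.

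Finally, serum vitamin C has the same repeated-measures wording under Aim 1. This point does not cover the primary endpoint, but if only Aim 2 changes, the plan should say why the methods differ.

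A reader might infer that the planned analysis is biased. It is not: arms are randomised, so change scores and baseline adjustment estimate the same Month 3 difference. A reader might also infer that the 80% power figure is wrong, but it reproduces.

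**Conclusion.** The point holds as a modest gain in precision on secondary endpoints, and as nothing stronger. For the Month 3 contrast, baseline adjustment beats the two-occasion analysis unless the slope of Month 3 on baseline is close to 1. With equal SDs the interval is about 12% to 4% narrower for rho 0.5 to 0.8, falling to nil at 0.95. The gain is larger if scores are less spread at Month 3 than at baseline, and about nil at rho 0.7 to 0.8 if they are 20 to 25% more spread.

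It would go too far to say that ANCOVA is more powerful than any repeated-measures ANOVA. A four-occasion interaction test matches it when the effect is full from Month 1 and rho is 0.7 or 0.8. I have high confidence in the direction and the cap on the loss. The percentages are conditional on the assumed rho and SD ratio.

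**What to change.** In Section 9, Aim 2, make the target for symptom burden and HRQOL the difference between each vitamin C arm and placebo at Month 3, with 95% confidence interval. Estimate it by ANCOVA of the Month 3 score on arm (three levels) and baseline score, in everyone randomised with both scores, analysed in the arm assigned. The same wording can cover cardiac function and oxidative stress, which are measured only at baseline and Month 3.

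State that the Month 1 and 2 scores are reported descriptively. Alternatively, to keep participants who miss Month 3, name in advance one mixed model of the Month 1 to 3 scores in place of the ANCOVA, with arm, month, arm-by-month, baseline and baseline-by-month. The last term should stay: with a single baseline slope and correlation that decays over time, the Month 3 variance is about 5 to 7% above ANCOVA in large samples.

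Cost: SAP wording and one degree of freedom (a few more for the mixed model). No new data, patients or software.

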## 7. MEASUREMENTS AND STUDY EVALUATIONS

**Serum vitamin C level.** We will measure participant's serum vitamin C level at baseline and Month 3 to measure the effect of vitamin C supplementation. Sample vitamin C will be measured in serum using MyBioSource ELISA kits.

**Symptom burden.** Physical symptom burden will be measured using items from the Memorial Symptom Assessment Scale—Heart Failure (MSAS-HF). The MSAS-HF is an 8-item questionnaire adapted from Portney's Memorial Symptom Assessment Scale that is designed to provide multidimensional information about HF symptoms experienced by patients with HF. Patients will be first asked if the symptom was present during the previous 7 days. If present, three characteristics of each symptom will be rated: frequency of symptom, severity of symptom, and degree of symptom distress. Frequency is rated on a scale from 1 to 4 (rarely to almost constantly), severity rated on a scale from 1 to 4 (mild to very severe) and distress rated on a scale from 0 to 4 (not at all to very severe). Burden score for each symptom can range from 0 (no burden) to 12 (greatest symptom frequency, severity, and distress). The scale has good reliability, ranges of 0.73-0.92 in patients with HF.

**Health-related quality of life (HRQOL).** The Minnesota Living with Heart Failure questionnaire (MLHFQ) is a measure of HRQOL that assesses the patient's perceptions of the

influence of HF on physical and emotional aspects of life. The 21 items are summed with higher scores indicating worse HRQOL. The questionnaire has been widely used to measure quality of life in this population. Researchers have demonstrated evidence for validity and reliability (Cronbach's alphas ranging from .88 to .93). The MLHFQ was used in our study that demonstrated a significant relationship between vitamin C deficiency and HRQOL, as well as between HRQOL and re-hospitalization or mortality.

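### Repeated-measures ANOVA for symptom burden and HRQOL excludes patients who leave after Month 2 despite their on-study scores, and the plan does not say which of the four occasions enter the model

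*Combined protocol and SAP*

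**What the plan says.** Section 3 (Design) of the combined protocol and SAP schedules in-person assessments at baseline and Month 3 and adds: "HF symptom burden and HRQOL will also be measured at Month 1 and 2 by phone". Sections 5 and 6 repeat this schedule, so these two outcomes have four planned occasions.

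Section 9 (Aim 2) gives the analysis. For symptom burden: "we will use repeated measure of ANOVA to detect differences in symptom burden from baseline to 3-month follow-up". For HRQOL, in one sentence with two other outcomes: "we will use repeated measure of ANOVA to detect differences in HRQOL (cardiac function, and oxidative stress) from baseline to 3-month follow-up". On software it says only "All data analyses will be performed using SPSS 24.0", without naming a procedure.

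Section 9 does not list the occasions in the time factor. It defines no analysis set, missing-data rule or dropout allowance. The same time phrase is used for the primary endpoint ("we will use repeated measure of ANOVA to detect differences in the serum vitamin C level from baseline to 3-month follow-up"), and section 7 has that endpoint measured on two occasions only: "serum vitamin C level at baseline and Month 3 to measure the effect of vitamin C supplementation".

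**The concern.** Classical repeated-measures ANOVA (GLM Repeated Measures in SPSS) works on one complete row per patient. A patient with a gap on any occasion in the time factor is left out. This is a property of the method and is not stated in the documents, but with no other rule given it becomes the working rule.

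For these two outcomes the trial obtains scores that this method cannot use. A patient who leaves after Month 2 has given a baseline score and two on-study scores, and none of them reaches the arm comparison. Each patient lost is 1/14, or about 7%, of an arm. Section 3 says the pilot's effect-size estimates are meant to inform a later trial, so a completers-only estimate would be carried forward.

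**Working it through.** **Inputs**
- Patients: "A total of 42 participants (14 per group) will be randomly assigned" (section 3).
- Occasions for symptom burden and HRQOL: four (sections 3, 5 and 6).
- Power statement (section 9): "With 42 patients (14 in each group) and an alpha level of .05, the power of the ANOVA F test" is put at 80% for an effect size of 0.5.
- Missing rate: none given; attrition is only something to be observed. I assume *m* = 5%, 10% or 15% missed at each of the three follow-up contacts, with baseline complete.

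**Step 1. The plan's own figure.** Take a one-way F test with 3 groups, f = 0.5, df 2 and 39, and noncentrality 42 × 0.5² = 10.5. Power is 80.3%, against 80% stated. The figure reproduces only with all 42 analysed, so it contains no allowance for loss. The plan names neither the effect-size index nor the endpoint, and the figure matches a one-way test rather than a group-by-time test.

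**Step 2. Who is kept, by pattern.**

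| Scores obtained | ANOVA, four occasions | ANOVA, baseline and Month 3 | Mixed model, all scores |
|---|---|---|---|
| All four | kept | kept; Months 1 and 2 unused | all four used |
| One call missed, Month 3 present | excluded | kept; remaining phone score unused | all three used |
| Left after Month 2 | excluded | excluded | baseline, Months 1 and 2 used |

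The last row does not depend on the reading. The second row does.

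**Step 3. Counts if contacts are missed independently.** Four occasions keep 42 × (1 − *m*)³; two keep 42 × (1 − *m*).

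| *m* | Four occasions | Two occasions | Difference: Month 3 score present but excluded by four |
|---|---|---|---|
| 5% | 42 × 0.857 = 36.0 | 39.9 | 3.9 |
| 10% | 42 × 0.729 = 30.6 | 37.8 | 7.2 |
| 15% | 42 × 0.614 = 25.8 | 35.7 | 9.9 |

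Patients with at least one follow-up score number 42 × (1 − *m*³) = 42.0, 42.0 and 41.9.

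**Step 4. Counts if the only loss is permanent dropout.** Everyone with a Month 3 score then also has Months 1 and 2. If 5%, 10% or 15% have gone by Month 3, both readings keep 39.9, 37.8 or 35.7, and the difference in Step 3 vanishes. What remains is the unused scores of the leavers: at 10%, 42 × 0.10 = 4.2 patients.

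**Step 5. Illustration on the plan's own power scale.** Putting the Step 3 counts into the Step 1 test gives 73.0%, 64.6% and 55.7% for four occasions, and 78.0%, 75.4% and 72.5% for two. These only show the scale of loss, because the plan's power statement is not tied to these outcomes or to this test.

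**The case against.** The best reply is that the text leans towards two occasions. The same time phrase is used for serum vitamin C, and HRQOL shares its sentence with cardiac function and oxidative stress; all three are measured only at baseline and Month 3. On that reading a missed call removes nobody. This stands. A reader might infer that one missed monthly call drops a patient, but the documents support that only if Months 1 and 2 are levels of the time factor. The 36, 31 and 26 figures carry the same condition, and they also assume independent misses, which the documents do not give and which produce a wider gap than pure dropout does.

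A reader might also infer that the excluded patients are sicker or intolerant of the tablets, so that the result is biased. That is possible, but the documents do not show it. Section 8 treats stopping the tablets and withdrawing from the study as separate steps, and the exclusion criteria remove NYHA class IV and stage D disease.

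Nor do leavers vanish from the trial: attrition is an Aim 3 outcome, and adverse events are asked about at each call. The visit window in section 4 and the phone or mail fallback in section 6 may reduce missing Month 3 scores. None of these is an analysis rule, and none brings a leaver's Month 1 and 2 scores into the Aim 2 comparison.

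Finally, these are secondary outcomes in a feasibility pilot. That limits the stakes, but the change needs no new data.

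**Conclusion.** The concern holds in a limited form. For symptom burden and HRQOL, the stated method excludes any patient who leaves after Month 2, on either reading, although on-study scores exist. Beyond that, the cost depends on a choice the plan leaves open: four occasions also exclude patients with a missed call, while two leave every phone score out of the comparison.

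Under the assumed 5% to 15% missed independently per contact, about 36 to 26 of 42 patients are kept with four occasions and about 40 to 36 with two. Under purely monotone dropout the readings do not differ. The direction and size of any bias cannot be established from the documents.

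The point does not extend to serum vitamin C, cardiac output or isoprostane, which have no intermediate scores to recover. It should be acted on because a better method is available at little cost.

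**What to change.** For symptom burden and HRQOL, replace repeated-measures ANOVA in section 9 with a linear mixed model for repeated measures (SPSS MIXED, REML) on all available scores of all randomised patients:
- Name all four occasions, and keep baseline as an outcome occasion so that every patient contributes.
- Include arm, month and arm-by-month terms.
- Use an unstructured covariance, with a prespecified simpler fallback such as compound symmetry if it does not converge.
- Report the Month 3 arm contrasts in change from baseline as the result.
- State the missing-at-random assumption.
- Show the complete-case ANOVA as a sensitivity analysis, naming the occasions it uses.

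The cost is revised SAP wording, slightly more analysis work, and a different procedure in software already chosen. The main downside is that an unstructured matrix for four occasions has 4 × 5 / 2 = 10 parameters to estimate from 42 patients, so the fallback may be needed. The model does not replace missing Month 3 scores, and the complete-case ANOVA does not test departures from missing at random. The gain is that scores already collected inform the comparison.
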